### 5.3 SCREEN FAILURES

Screen failures are defined as participants who go through screening process for eligibility but are not subsequently entered in the study. Individuals who do not meet the criteria for participation in this trial (screen failure) at time of screening because of meeting one or more exclusion criteria that are likely to change over time may be rescreened. Examples include pain that does not meet intensity or frequency threshold, recent or planned surgery outside of defined threshold, and currently undergoing cognitive behavioral therapy at time of screening visit. Rescreened participants will be assigned the same participant number as for the initial screening.

### 5.4 STRATEGIES FOR RECRUITMENT AND RETENTION

We will be using thoughtful recruitment and allocation methods to minimize bias. We will attempt to include a diverse group of participants for this study, with intentional recruitment to reflect diversity in age, race, geographic location and pelvic pain conditions.

We will contact both intervention and control patients with text or email prompts to visit their respective website on prespecified basis with goal of increasing program utilization and study retention. In the first 12 weeks of the study (active phase), participants will receive a weekly text or email prompt directing them to a specific module or portion of their respective website. During the remaining time in the study (maintenance phase), all participants will receive monthly text or email prompts to visit their respective website. Details of the prompts for the intervention and control groups are included in 8.2 Study evaluation and procedures.

We are unable to track website utilization for specific users. However, we will send an email link to a survey once per month which will ask which skills (from the *Managing Symptoms* section of the website) they used in the last month regardless of whether they visited that module in the site. We assume that some patients will need repeated exposure to skills to gain mastery and incorporate into their routine, whereas other patients may visit a module once and be able to incorporate it into regular practice.

Patients will receive a questionnaire battery at 3-month interval (primary endpoint) and 6-month interval (secondary endpoint). Patients will receive a reminder email if they have not completed the survey or questionnaire within 4 days, 7 days, and 14 days. Only three reminders will be sent per survey/questionnaire, with the exception of the 6-month survey, for which patients may receive one additional reminder at 21 days.

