### 7.3 LOST TO FOLLOW-UP

Patients will receive an email with a link to questionnaires and utilizations surveys at each time point specified above. If questionnaires are not completed within 4 days, an automatic reminder email will be

sent. If questionnaires are not completed within 7 days, a study member will call with a reminder. If questionnaire is not completed with 14 days, a study member will call with another reminder. Patient will be considered lost to follow up if they fail to complete the 6-month questionnaire within 21 days after survey invitation.

We will not exclude or dismiss patients based on completion of 6-month questionnaire or monthly utilization survey as these are not essential for the primary outcome.

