### 9.3 POPULATIONS FOR ANALYSES

We will use an intent to treat analysis. Primary outcome (pain interference) will be assessed at 3-months and 6-month data will only contribute to secondary outcomes. Given this, we will plan carry the last observation forward (either 3-month or baseline) for patients who are lost to follow up at 6-months.

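### The optional fourth reminder is reserved for the 6-month questionnaire, not the primary 3-month one, and it falls on the day the patient is labelled lost to follow-up

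*Combined protocol and SAP*

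**What the plan says.** Section 5.4 sets the common schedule: "Patients will receive a reminder email if they have not completed the survey or questionnaire within 4 days, 7 days, and 14 days". It then sets the cap, "Only three reminders will be sent per survey/questionnaire", and makes one exception: "with the exception of the 6-month survey, for which patients may receive one additional reminder at 21 days". I read the exception as meaning the 6-month questionnaire rather than the sixth monthly utilization survey, because section 7.3 also uses the word survey for the invitation to that questionnaire.

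Section 7.3, repeated in section 8.2, gives the only lost-to-follow-up definition in the plan: "Patient will be considered lost to follow up if they fail to complete the 6-month questionnaire within 21 days after survey invitation". Neither section mentions a fourth reminder, and neither gives a cutoff for the 3-month questionnaire. Section 7.3 itself ranks the two time points by their bearing on the main endpoint: "We will not exclude or dismiss patients based on completion of 6-month questionnaire or monthly utilization survey as these are not essential for the primary" (the quote stops one word before the sentence ends).

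Section 9.3 agrees on the ranking ("Primary outcome (pain interference) will be assessed at 3-months and 6-month data will only contribute to secondary outcomes") and attaches an analysis rule to the label: "we will plan carry the last observation forward (either 3-month or baseline) for patients who are lost to follow up at 6-months". The schedule in section 1.3 places the questionnaires at Day 90 ± 14 and Day 180 ± 14.

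**The concern.** There are two separate faults.

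First, the reminder cap is the wrong way round. A missing 3-month answer is the costlier loss, for three reasons:
- The primary comparison and Hedges' g in section 9.4.2 both rest on it.
- Replacement (sections 4.1, 7.2 and 8.2) covers only patients who withdraw before the 3-month questionnaire is sent, so a later non-responder cannot be replaced.
- The carry-forward rule covers 6 months only. For 3 months the plan offers only unnamed sensitivity analyses once more than 5% are missing.

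The plan gives no reason for allowing the extra reminder only at the less important time point.

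Second, the fourth reminder and the lost-to-follow-up cutoff share a day. A patient who responds to that reminder on day 22 has returned a real 6-month answer but already carries the label that triggers carry-forward. The plan does not say which value is analysed. Left open, that choice would be made after the data are seen.

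**Working it through.** The plan states no power, dropout rate or reminder yield, so it has no figure to reproduce. The check is a comparison of dates, followed by an illustration of precision.

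**Reminders and cutoff** (sections 5.4, 7.3 and 8.2; all days counted from the invitation, which is an assumption for the reminder days)
- 3 months: days 4, 7 and 14, so 3 reminders. No cutoff is stated.
- 6 months: days 4, 7, 14 and optionally 21, so up to 4 reminders. The cutoff is day 21.
- Time from the last 6-month reminder to the cutoff: 21 − 21 = 0 days. At most the rest of day 21 remains.

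**Study days against the windows in section 1.3**
- 3-month window: 90 ± 14 = Days 76 to 104. With an invitation on Day 90, the last reminder falls on 90 + 14 = Day 104, the last day of the window. A day-21 reminder would fall on Day 111, outside it. With an invitation on Day 76, it would fall on Day 97, inside it.
- 6-month window: 180 ± 14 = Days 166 to 194. With an invitation on Day 180, the fourth reminder and the cutoff both fall on Day 201, 7 days past the window. With an invitation on Day 166, both fall on Day 187, inside it.

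**The 5% trigger in section 9.4.2**
- 0.05 × 69 = 3.45, so 4 missing primary outcomes start sensitivity analyses.

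**Possible gain at 3 months (assumed rates)**
- Assume 10% to 20% have not answered after the day-14 reminder: 6.9 to 13.8, or about 7 to 14 of 69.
- Assume a fourth reminder recovers a quarter to a third of them: 7 × 0.25 ≈ 2, up to 14 × 0.33 ≈ 5.
- The 95% half-width for a difference in means, in SD units, is 1.96 × √(1/n_I + 1/n_C). At 2:1 with N analysed, n_I = 2N/3 and n_C = N/3, so this is 1.96 × √(4.5/N).

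| Case | N without reminder | Half-width | N with reminder | Half-width | Change |
|---|---|---|---|---|---|
| 10% missing, 2 recovered | 62 | 0.528 | 64 | 0.520 | 0.008 |
| 20% missing, 5 recovered | 55 | 0.561 | 60 | 0.537 | 0.024 |

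At full retention (N = 69) the half-width is 0.50 SD. The gain in precision is therefore about 0.01 to 0.02 SD. Any reduction in bias from non-response cannot be calculated from the documents.

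**Late 6-month answers: the sections together**
- Sections 7.3 and 8.2: not complete within 21 days means lost.
- Section 9.3: lost at 6 months means an earlier value is carried forward.
- Section 7.3: patients are not excluded or dismissed over 6-month completion. This concerns participation and does not say which value is analysed.
- No section says that an answer received after day 21 is dropped, and none says that it is kept.

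**The case against.** The strongest case against this is that the 3-month questionnaire is protected in other ways. Section 10.1.9 does not exempt a missing primary outcome from being a protocol deviation, as it does other missing surveys. Sections 4.1 and 8.2 define study completion by the 3-month questionnaire. Sections 7.3 and 8.2 describe personal calls at days 7 and 14. Prompts are weekly through week 12 in both arms and only monthly afterwards. Patients who withdraw before the 3-month questionnaire is sent are to be replaced where possible. The extra reminder is also optional, and stopping at day 14 fits the primary window for an invitation on Day 90.

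Much of this stands. A reader might infer that the trial as a whole pursues primary data less hard than 6-month data. The documents do not support that: the difference is one optional message. But none of these provisions removes the lower cap. The window does not explain it either, because at 6 months the plan allows a reminder on Day 201 against a window that ends on Day 194.

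A reader might also infer that late 6-month answers are discarded. No section says so. It follows only from joining the section 7.3 definition to the section 9.3 rule, and an answer on day 21 itself still counts as in time. What stands is the zero-day gap and the lack of a rule for answers that come after it.

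**Conclusion.** The point holds in limited form and is worth correcting, though it does not threaten the trial. By the written rule, the primary time point has a cap of three reminders against up to four at 6 months, without justification. The fourth reminder coincides with the lost-to-follow-up cutoff, assuming both run from the invitation. The treatment of later answers is unstated, and the literal reading would replace them.

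The size is modest. The 0.01 to 0.02 SD gain rests entirely on assumed non-response and recovery rates, in a pilot that section 9.2 says is not powered. The effect size estimate is nonetheless a main product of the trial, and 4 missing primary outcomes pass the plan's own trigger. The 6-month fault does not touch the primary comparison: those data are secondary in section 9.3 and exploratory in sections 9.4.2 and 9.4.3.

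**What to change.** 1. In section 5.4, allow the day-21 reminder for the 3-month questionnaire as well, in both arms.
2. In sections 7.3 and 8.2, set the lost-to-follow-up cutoff at a fixed date after the last reminder, for example 28 days after invitation. Give the 3-month questionnaire a closing date too.
3. In section 9.3, state that any answer received before closing is analysed as observed, and that carry-forward applies only when no answer was received.
4. Flag answers outside Day 90 ± 14 or Day 180 ± 14, and report the primary result with and without the late 3-month answers.
5. Reconcile the reminder mode: section 5.4 has emails at days 7 and 14, while sections 7.3 and 8.2 have calls on those days.

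The cost is one message per non-responder and a wording change. The downside is a wider spread in the timing of 3-month answers, which may differ by arm; item 4 is there to show whether that matters. With an invitation on Day 90, a 28-day closing date is Day 118. That lies inside the Day 120 ± 14 contact window (Days 106 to 134), so the 3-month reminders may overlap with the month-4 survey and the two mailings need coordinating.

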## 5.5 COMPENSATION

All patients will receive \$50 for completion of each of the three questionnaires (baseline, 3-month, 6-month). Patients in control group who complete all portions of the study will receive a total of \$150.

In addition, intervention patients will receive \$5 for each of the six utilization surveys completed. Intervention patients who participate in a focus group at 3-months will receive \$100. Therefore, patients in intervention group who complete all portions of the study will receive a total of \$180-280, depending on focus group participation.

All compensation will be managed by a study team member in conjunction with the University of Michigan Human Subjects Incentive Program (HSIP). Patients will be sent a gift card at time of completion of the baseline questionnaire. Additional compensation payments will be virtually loaded to the gift card upon completion of additional questionnaires.

## 6 STUDY INTERVENTION(S) OR EXPERIMENTAL MANIPULATION(S)

### 6.1 STUDY INTERVENTION(S) OR EXPERIMENTAL MANIPULATION(S) ADMINISTRATION

#### 6.1.1 STUDY INTERVENTION OR EXPERIMENTAL MANIPULATION DESCRIPTION

As this is an exploratory study, we will incorporate several types of treatment modalities – cognitive/behavioral, acupuncture, physical therapy, and physical activity – and allow patients to utilize each as they wish. However, we will utilize an established tailoring program to direct participants to particular modules or skills that are likely to be most relevant for their individual symptoms and characteristics. This tailoring program utilizes the baseline patient reported outcome measures (PROMIS 29+2). Responses to each of these measures will be scored to obtain a T-score, which will then be ranked in order of divergence from population mean to represent relative burden of each factor. All patients will receive prompts to the same modules during the first four weeks of the active phase. However, prompts during the next 8 weeks of the active phase will correspond to the rank order of the baseline measure T-scores, directing patients to modules that address each of these factors. During the maintenance phase of the study, all patients will receive the same monthly prompt to visit the Monitoring Progress symptom tracker subpage of the website.

Evaluating preliminary effectiveness of the program will inform how we might adapt the intervention for future studies. This will also help explore preliminary information about patient phenotyping – whether certain factors predict which patients tend to respond most robustly to various treatments.

### 6.2 FIDELITY

### 6.2.1 INTERVENTIONIST TRAINING AND TRACKING

There is no variability in this program itself as all intervention patients have access to the same web-based program. While patients will receive tailored or curated prompts to visit specific modules in the program based on their individual symptom burden, the website itself is static.

### 6.3 MEASURES TO MINIMIZE BIAS: RANDOMIZATION AND BLINDING

Random allocation will occur in 2:1 ratio (intervention:control) utilizing permuted blocks of 4 without stratification. Allocation concealment will be ensured using computer generated central randomization and will occur after patient has signed the consent form. Enrollment will occur on a rolling basis until 69 patients have been enrolled. The study team member who generates random allocation sequence will not be involved in recruitment or enrollment.

Both patients and outcome assessors will be blinded to study group assignment. During recruitment, we will state that we are testing two different web-based approaches for self-management for chronic pelvic pain, so patients will not be aware of which study group they are enrolled in. Patients will be contacted at essentially the same intervals throughout the study period to further maintain blinding. We will attempt to blind the patient's CPP provider as to their group status but are unable to control the possibility that a patient mentions the intervention to their provider. We will ask providers not to comment about group status or discuss the intervention in detail with patients to maintain patient blinding to as great an extent as possible.

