## 4 STUDY DESIGN

### 4.1 OVERALL DESIGN

This Stage 1 intervention will conduct a pilot randomized controlled trial to evaluate preliminary effectiveness of a web-based, self-management program for patients with CPP and phenotypic factors that predict positive response. Our overall hypothesis is patients with CPP who have access to this intervention will demonstrate improved in pain, physical function, and quality of life.

This trial will be conducted at Michigan Medicine (single site) and all patients will recruited from the Chronic Pelvic Pain and Endometriosis referral clinic.

Random allocation will occur in 2:1 ratio (intervention:control) utilizing permuted blocks of 4 without stratification. Allocation concealment will be ensured using computer generated central randomization and will occur after patient has signed the consent form. The study team member who generates random allocation sequence will not be involved in recruitment or enrollment. Patients will be blinded to their group assignment. Study team members involved in outcome assessment will be blinded to group assignment. The patient's CPP provider who will continue to provide usual care for pelvic pain will also be blinded from group assignment.

Patients will be randomized to participation in a 6-month web-based, integrative self-management program (<https://www.mypelvicplan.com/>) in addition to usual care as determined by the patient's CPP provider (intervention group), or to a web-based symptom monitoring program (<https://monitoringprogress.org/>) in addition to usual care (control group). The intervention is comprised of a self-guided program that combines education on several individual conditions that often contribute to CPP, and will include instruction on cognitive and behavioral restructuring, self-administration of acupressure, engaging in physical activity, and a brief introduction to pelvic floor physical therapy techniques.

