## 8 STUDY ASSESSMENTS AND PROCEDURES

### 8.1 SCREENING PROCEDURES

We will be using thoughtful recruitment and allocation methods to minimize bias. Our group of specialty-trained gynecologists see approximately 150 patients per month in this referral clinic. Each returning patient will receive a brochure containing a brief description of the study and an interest sheet during their check-in. A physician may assess interest if they feel that the patient may be an appropriate candidate. A study team member will also screen patients scheduled for return visits in the clinic and contact potentially eligible patients via text or email to inform them that they may be eligible for the study. We will not recruit new patients during this pilot study as patients often initiate a number of new treatments following the initial visit and we suspect that it might be more challenging to differentiate effect of the intervention versus treatment plan in this population.

A study team member will contact interested patients to assess eligibility and confirm interest and obtain consent (electronic). Potential subjects will be contacted up to seven times (by telephone, text, portal message, or email) in order to establish contact. Entry as a subject requires passing a telephone screen to confirm eligibility.

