### 8.2 STUDY EVALUATION AND PROCEDURES

Once eligibility and interest are confirmed, the study team member will send an email link to an electronic version of the consent form. The study team member and patient will review study consent verbally over the telephone and answer any questions. Consent forms describing in detail the study intervention, study procedures, and risks will be given to the participant. Consent forms will be signed and stored electronically. We have elected to perform this combination of verbal and online consent as opposed to a face-to-face consent as the majority of patients from our referral clinic travel between 1-4 hours to reach our clinic. One of goals of this intervention is to expand access and limit barriers related to travel that our patients typically encounter. Therefore, we felt that requiring subjects to return for a visit specifically for a face-to-face consent would impose too great a burden for many participants, and that this approach was reasonable given the remote contact utilized in other aspects of this study.

Random allocation will occur in 2:1 ratio (intervention:control) utilizing permuted blocks of 4 without stratification. Allocation concealment will be ensured using computer generated central randomization and will occur after patient has signed the consent form. The study team member who generates random allocation sequence will not be involved in recruitment or enrollment. Patients will be blinded to their group assignment. Study team members involved in outcome assessment will be blinded to

group assignment. The patient's specialty gynecologist who will continue to provide usual care for pelvic pain will also be blinded to group assignment.

Enrollment will occur on a rolling basis until 69 patients have been enrolled. We anticipate that we will likely need to screen approximately 200 patients in order to enroll 69 participants over an 18-month period. We will attempt to recruit a diverse group of patients, with attention to diversity in race, ethnicity, age, education level, rural vs urban locality, sexual orientation, and gender identification.

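### One fixed, small block size is printed in the protocol of a single-site, unstratified trial, and nothing states that staff who screen and consent are kept from seeing earlier allocations

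*Combined protocol and SAP*

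**What the plan says.** Section 6.3 states: "Random allocation will occur in 2:1 ratio (intervention:control) utilizing permuted blocks of 4 without stratification". Sections 4.1 and 8.2 repeat this. Section 4.1 describes a single site, and recruitment is continuous: "Enrollment will occur on a rolling basis until 69 patients have been enrolled".

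The safeguards are these:

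- **Concealment (6.3):** "Allocation concealment will be ensured using computer generated central randomization and will occur after patient has signed the consent form".
- **Separation of roles (6.3, 8.2):** "The study team member who generates random allocation sequence will not be involved in recruitment or enrollment".
- **Blinding (6.3):** "Both patients and outcome assessors will be blinded to study group assignment". The patient's pelvic pain provider is also to be blinded. Sections 4.1 and 8.2 state this outright, while 6.3 says only that it will be attempted.

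Section 8.1 gives a study team member the tasks of contacting patients, checking eligibility and obtaining consent. No section says whether that person can see the arms of patients already randomized.

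**The concern.** Central randomization hides the list. It does not hide the end of a block from someone who knows the block length and has seen the block's earlier entries. With one site, no strata and one published block length, there is only one short pattern to follow.

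Some members of the team must know the arm. Section 6.4 sends monthly utilization surveys to the intervention group only, and section 8.2 draws focus groups from that group. Recruitment also leaves room for discretion. Section 8.1 allows a physician to judge whether a patient is a suitable candidate, and it states: "Potential subjects will be contacted up to seven times (by telephone, text, portal message, or email) in order to establish contact". Sections 5.4 and 8.2 add deliberate recruitment for diversity.

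If the next arm could be foreseen, patients with a better outlook could be approached when an intervention slot was due, even unintentionally. The primary analysis in 9.4.2 is a t-test on a self-reported 3-month score with no baseline adjustment, so such selection would enter the arm difference undiminished. It would also enter the Hedges' g that 9.4.2 reserves for planning the efficacy trial, which 9.2 names as a main purpose of the pilot.

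**Working it through.** **1. The stated scheme.** The inputs are a 2:1 ratio, a block of 4, no strata and N = 69 (6.3). The plan gives no predictability figure to reproduce. The scheme itself cannot be built: 4 × 2/3 = 2.67 is not a whole number, and 69/4 = 17.25 blocks. Blocks of 3 would fit exactly (69/3 = 23 blocks, 46:23). The share must therefore be worked out for each possible reading.

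**2. Definition.** An assignment counts as known when every remaining entry in its block is the same arm, given the block's length and composition and all its earlier entries. I is intervention and C is control.

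**3. Enumeration over equally likely orderings.**

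| Reading | Known entries per ordering | Mean | Share known |
|---|---|---|---|
| 3 at 2:1 | CII 2, ICI 1, IIC 1 | 4/3 = 1.333 | 1.333/3 = 44.4% |
| 4 at 3:1 | CIII 3, ICII 2, IICI 1, IIIC 1 | 7/4 = 1.75 | 1.75/4 = 43.8% |
| 4 at 2:2 | IICC 2, CCII 2, four others 1 each | 8/6 = 1.333 | 1.333/4 = 33.3% |

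Blocks of 4 could average 2:1 if two-thirds were 3:1 and one-third 2:2, since (3 + 3 + 2)/12 = 2/3.

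- If the order of compositions is known, the share is (1.75 + 1.75 + 1.333)/12 = 40.3%.
- If the order is random and concealed, only four orderings contain a certain entry: IIIC (probability 2/3 × 1/4 = 3/18, 1 known), CCII (1/18, 2 known), ICCI (1/18, 1 known) and CICI (1/18, 1 known). The mean is (3 + 2 + 1 + 1)/18 = 7/18 = 0.389, and 0.389/4 = 9.7%.

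**4. Alternatives at an exact 2:1.** A fixed block of 6 gives 1.733/6 = 28.9%. Random sizes were simulated on lists of 69, with an observer who knows the menu of sizes and updates on all past entries. Sizes 3/6 give about 9%, and 3/6/9 about 4%.

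**5. What steering could do (illustration).** In the 3:1 and 2:1 readings half of the intervention slots are known (1.5/3 and 1.0/2). Assume that patients steered into known intervention slots score 2.5 points better, and let s be the fraction of known intervention slots steered. Then bias = s × 0.5 × 2.5. The figure 2.5 is borrowed from the responder threshold in 9.4.2. The documents give no SD, so 6 to 10 is assumed. Two-sided type I error comes from the noncentral t with 67 df and noncentrality bias/(SD × √(1/n₁ + 1/n₂)). For example, at 46:23 with SD 6, 1.25/(6 × 0.2554) = 0.816, which gives 12.7%.

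| s | Bias (points) | Bias in SD units | Type I error, 46:23 and 52:17 |
|---|---|---|---|
| 1 | 1.25 | 0.13–0.21 | 7.3–12.7% |
| 1/2 | 0.63 | 0.06–0.10 | 5.6–6.9% |
| 1/4 | 0.31 | 0.03–0.05 | 5.1–5.5% |

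**The case against.** The strongest reply is that the protocol already has the main safeguards: central computer randomization, allocation only after signature, and a sequence generator with no part in recruitment. Prediction needs every earlier assignment in order, the block boundaries, and knowledge of which pending patient will sign next. Consent is signed electronically from an emailed link, and several patients may be in contact at once, so timing one patient to one slot is not easy. Seven contacts is a ceiling for reaching someone, not evidence of timing. Physicians who suggest candidates are themselves meant to be blinded. The study is also an unpowered pilot.

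Much of this stands. It makes the percentages upper bounds and makes full steering unlikely. It does not remove the gap. Allocation after consent prevents switching a patient who has already signed, but not choosing whom to pursue next. Being unpowered does not protect an effect-size estimate from bias.

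Two stronger readings should be resisted:

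- A reader might infer that recruiters are unblinded, because someone must handle websites, prompts, surveys and focus groups. The documents do not say that those people also recruit, or that access and prompts are set up by hand.
- A reader might quote 44% as the predictability of the printed scheme. The printed scheme is impossible, and 44% needs a substitution that the protocol does not make.

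**Conclusion.** The concern holds in a limited form. One fixed, small block size is published for a single-site, unstratified trial, and recruiting staff are not stated to be kept from earlier allocations. If they can see them, up to about 33–44% of assignments could be known in advance with a fixed block composition, or about 10% with a concealed mix of blocks of 4. Which figure applies cannot be settled until the ratio and block size are reconciled.

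The effect on the results cannot be fixed from the documents. A type I error of 7–13% requires every known intervention slot to be steered, a 2.5-point prognostic gap and an assumed SD of 6–10. In the plan, 2.5 is a within-patient improvement, not a difference between patients. Steering half of the known slots gives 5.6–6.9%. Nothing shows that steering would occur. The case for acting is that the exposure is avoidable at almost no cost, and that correcting the sentence to a fixed block of 3 would leave the share at 44%.

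**What to change.** Reconcile the ratio and the block size in 4.1, 6.3 and 8.2, stating the scheme actually used. In the same edit, replace the reference to blocks of 4 with: *permuted blocks of randomly varying size, each a multiple of 3, with sizes known only to the person who generates the list*. Keep the sizes in a restricted document. Add one sentence: *staff who screen and consent patients do not see earlier allocations*.

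The cost is a regenerated list, one changed sentence in three sections, and an access rule if none exists yet. No extra patients are needed. The downside is a small imbalance if enrolment stops in mid-block. With sizes up to 9 (6:3), the worst case is six intervention entries first, when four are expected, or three control entries first, when two intervention entries are expected. Either is two patients away from an exact 2:1 split.
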